5.2. Treatment Allocation

On the day of enrollment, pregnant women will be referred to a study pharmacist responsible for treatment allocation. The study pharmacist will assign treatment arms as follows:

1. Select next available envelope
2. Note treatment number on the outside of the envelope
3. Write date, time, and study number on the outside of the envelope
4. Open envelope

5. Remove form containing code for treatment arm and date, time, and study number (transferred to form via carbon paper inside of envelope)
6. Store form in lockable file box in study pharmacy
7. Record onto the treatment allocation master list the study number, enrollment date, treatment assignment code, treatment arm, and study medications to be given during pregnancy and infancy
8. Store treatment allocation Master list in a lockable cabinet in study pharmacy
9. Record treatment number in the study participant's file

5.3. Study Drug Dosing and Formulations

During pregnancy, women will be given 1 of 3 treatment regimens: 1) SP given 3 times during pregnancy, 2) DP given 3 times during pregnancy, or 3) DP given every 4 weeks during pregnancy. Each treatment with SP will be given as a single dose consisting of 3 full strength tablets. Each treatment with DP will consist of 3 full strength tablets given once a day for 3 consecutive days. In addition, placebos will be used to mimic the identical dosing strategy such that every 4 weeks women will receive two pills on day 1 (SP and placebo, DP and placebo, or two placebos) followed by one pill on days 2 and 3 (DP or placebo). Two placebos will be used, one that mimics the appearance of SP and one that mimics the appearance of DP. Dosing schedules for each treatment regimen according to gestational age are presented in Appendix D. Details of the study drug formulations are included in Table 5.

During infancy, children will be given DP either every 4 weeks or every 12 weeks. Each treatment with DP will consist of half-strength tablets given once a day for 3 consecutive days according to weight based guidelines outlined in Appendix E. Infants randomized to receive DP every 12 weeks will receive placebo mimicking the dosing of DP every 4 weeks when they are not receiving study drug. Dosing schedules for each treatment regimen according to the child's age are presented in Appendix D.

Table 5. Drug formulation and labeling

Drug	Formulations	Trade name (Manufacturer)
Sulfadoxine-Pyrimethamine (SP)	500mg/25mg tabs	Kamsidar (KPI)
Dihydroartemisinin-Piperaquine (DP) Full strength tablets	40mg/320mg tabs	Duo-Cotexin (Holley-Cotec)
Dihydroartemisinin-Piperaquine (DP) Half strength tablets	20mg/160mg tabs	Duo-Cotexin (Holley-Cotec)

5.4. Blinding, Study Drug Administration, and Duration

Administration of all study drugs will be double blinded. All doses of study drugs will be prepackaged by a study pharmacist and administered by a study nurse blinded to the study participant's treatment regimen. All doses of SP (or SP placebo) administered will be directly observed in the clinic. For DP (or DP placebo), the first of the 3 daily doses will be directly observed in the clinic and the 2nd and 3rd daily doses will be administered at home using pre-packaged study drugs in opaque envelopes with dosing instructions written on the outside. For doses of study drugs administered in the clinic, if a study participant vomits the study drug within 30 minutes of administration, the drug will be re-administered. For doses of study drugs administered at home, if a study participant vomits the study drug within 30 minutes of administration or study drug is lost, the study participant will be instructed to come to the study clinic as soon as possible where the study drug will be re-administered/replaced. For pregnant women all doses of study drugs will be given between 16 and 40 weeks gestation and for children all doses of study drugs will be given between 8 and 104 weeks (2 years) of age as outlined in Appendix D.

5.5. Study Drug Accountability

The study pharmacist will maintain complete records of all study drugs received in the study pharmacy. Lot number and number of pills given to each study participant will be recorded. A registry of all study medication, current product labels, and Certificates of Analysis, provided by suppliers will be maintained within the regulatory binder for the study. The date received, lot number, expiration date, and date used will be recorded for each of the study medications. Monthly inventory of all study medications will be conducted and a record log of investigational medications will be kept at the study clinic.

6. SUBJECT MANAGEMENT

6.1. Subject Follow-up

Pregnant women will be scheduled to be seen in the clinic every 4 weeks during their pregnancy and 6 weeks following delivery. In addition, pregnant women will be instructed to come to the study clinic for all their medical care and avoid the use of any outside medications. Children will be scheduled to be seen in the clinic every 4 weeks and parents /guardians of children will be instructed to bring their child to the study clinic for all medical care and avoid the use of any outside medications. The study clinic will remain open 7 days a week from 8 a.m. to 5 p.m. Pregnant women and children who are not seen on the day of their regularly scheduled visits will be visited at home and instructed to come to the clinic as soon as possible.

Each time a study participant is seen in the clinic a standardized history and physical exam will be performed including temperature, pulse, and blood pressure measurement. Patients who are febrile (tympanic temperature $\geq 38.0^{\circ}\text{C}$) or report history of fever in the past 24 hours will have blood obtained by finger prick for a thick blood smear (in very young children, heel sticks may be substituted for finger pricks). If the thick blood smear is positive, the patient will be diagnosed with malaria. If the thick blood smear is negative, the patient will be managed by study physicians for a non-malarial febrile illness (Section 6.3). If the patient is afebrile and does not report a recent fever, a thick blood smear will not be obtained, except when following routine testing schedules (Section 6.5).

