Clinical Site	The study will be conducted in Tororo, Uganda. A designated study clinic will be located within the Tororo District Hospital Complex. The study clinic will be open daily from 8:00 am to 5:00 pm and after-hours care will be available at Tororo District Hospital.	
Selection Criteria	
Inclusion Criteria
 
 1. Pregnancy confirmed by positive urine pregnancy test or intrauterine pregnancy by ultrasound 2. Estimated gestational age between 12-20 weeks 3. Confirmed to be HIV- uninfected by rapid test 4. 16 years of age or older 5. Residency within 30km of the study clinic 6. Provision of informed consent 7. Agreement to come to the study clinic for any febrile episode or other illness and avoid medications given outside the study protocol 8. Plan to deliver in the hospital 
Exclusion Criteria:
 
 1. History of serious adverse event to SP or DP 2. Active medical problem requiring inpatient evaluation at the time of screening 3. Intention of moving more than 30km from the study clinic 4. Chronic medical condition requiring frequent medical attention 5. Prior SP preventive therapy or any other antimalarial therapy during this pregnancy 6. Early or active labor (documented by cervical change with uterine contractions) 	
Treatment assignment	HIV-uninfected pregnant and their unborn child(ren) will be randomized at the time of enrollment.	
Treatment arms	IPTp during pregnancy	Chemoprevention in children 2-24 months of age
	
 1. 3 dose SP 2. 3 dose DP 3. Monthly DP 	
 1. Monthly DP 2. 3 monthly DP
Follow-up and Diagnosis of Malaria	Study participants will be followed for all of their outpatient medical care in our study clinic. Pregnant women will be followed until 6 weeks postpartum and children will be followed until 36 months of age. Routine assessments will be performed in the study clinic for all study participants every 4 weeks. Patients presenting with a new episode of fever will undergo standard evaluation for the diagnosis of malaria.	

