Malaria Case Definitions	
Uncomplicated malaria (all of the following):
 
 1. Documented fever or history of fever in the prior 24 hours 2. Positive thick blood smear 3. Absence of complicated malaria 
Complicated malaria (any of the following):
 
 1. Evidence of severe disease with a positive thick blood smear (Appendix F) 2. Danger signs in children with a positive thick blood smear (Appendix F) 	

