6.2. Diagnosis and Management of Malaria

Patients found to have malaria based on laboratory confirmation will have a second finger prick for a thin smear (to determine parasite species), hemoglobin measurement using a portable spectrophotometer (HemoCue), and collection of plasma for future PK studies. All episodes of malaria will be classified as uncomplicated or complicated based on the following criteria:

Uncomplicated malaria (all of the following)

- 1) Fever ($\geq 38.0^{\circ}\text{C}$ tympanic) or history of fever in the previous 24 hours
- 2) Positive thick blood smear
- 3) Absence of complicated malaria

Complicated malaria (any of the following)

- 1) Evidence of severe malaria (Appendix F) and parasitemia
- 2) Danger signs present in children (Appendix F) and parasitemia

Episodes of malaria will also be classified into the following categories according to the timing of previous malaria episodes for treatment purposes:

1. New episodes of malaria will be defined as any first episode or any episode occurring > 14 days after the diagnosis of a previous episode
2. Treatment failures will be defined as any of the following:
 - a. Complicated malaria occurring 1-14 days after the diagnosis of a previous episode
 - b. Fever ($\geq 38.0^{\circ}\text{C}$ tympanic) or history of fever in the previous 24 hours with a parasite density \geq the parasite density of an episode of malaria diagnosed 2 days prior

- c. Fever ($\geq 38.0^{\circ}\text{C}$ tympanic) or history of fever in the previous 24 hours with a parasite density $\geq 25\%$ of the parasite density of an episode of malaria diagnosed 3 days prior
- d. Fever ($\geq 38.0^{\circ}\text{C}$ tympanic) or history of fever in the previous 24 hours with a positive thick blood smear of any parasite density occurring 4-14 days after the diagnosis of a previous episode

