All patients diagnosed with new episodes of uncomplicated malaria will be prescribed AL, the recommended first-line treatment in Uganda for children and pregnant women in their 2nd or 3rd trimester. Patients with complicated malaria will be prescribed quinine or artesunate according to national malaria treatment guidelines. Children who are less than 4 months of age or weigh $<5\text{kg}$, will be treated with quinine for uncomplicated malaria in accordance with the Uganda Ministry of Health Guidelines. Patients with treatment failure within 14 days following treatment with AL will be prescribed quinine according to national malaria treatment guidelines. Patients with treatment failure within 14 days following treatment with quinine or artesunate will be treated with quinine plus clindamycin or artesunate.

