6.3. Management of Non-Malaria Illnesses

Patients who are found to have illnesses other than malaria will receive standard-of-care treatment in the study clinic, according to standardized algorithms, or will be referred to the Tororo District Hospital. We will avoid the routine use of non-study medications with antimalarial activity, including tetracyclines, antifolates (with the exception of assigned chemopreventive regimens), and macrolide antibiotics, when acceptable alternatives are available. In addition, drugs with known risk of torsades de pointes or CYP3A inhibitors (Appendix K and L) will be avoided when prescribing treatment to pregnant women or children during the time they are taking study drugs. If the study clinician deems treatment with one of the drugs listed on Appendix K or L is required, the clinical management team will be consulted. During follow-up for non-malarial illnesses, blood smears will be done at the discretion of the study physician if the subjects are febrile (tympanic temperature $\geq 38.0^{\circ}\text{C}$) or report history of fever in the past 24 hours. If the blood smear is positive, the patient will be diagnosed with a new episode of malaria and managed per study protocol.

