6.5. Routine Assessments

Routine assessments will be done in the clinic every 4 weeks for both pregnant women and children. Study participants not seen in the clinic for their every 4 week routine visits will be visited at home and requested to come to the study clinic as soon as possible. Pregnant women and children will receive standards of care as designated in the Uganda MOH guidelines (Appendix G). Routine antenatal care will include screening and treatment for sexually transmitted Infections, blood pressure assessment, urine dipstick for proteinuria, prescription of iron, folate, multivitamins and mebendazole. Routine care in children will include immunizations, vitamin A supplementation, and management of anemia using Integrated Management of Childhood Illness (IMCI) guidelines. During routine assessments subjects will be asked about visits to outside health facilities and the use of any medications outside the study protocol. The study protocol will be reinforced with discussion regarding the need to come to the study clinic promptly upon the onset of any illness and to avoid use of outside medications. Standardized assessment of adherence will also be done for study drugs administered at home and ITN use. A routine history and physical exam will be performed using a standardized clinical assessment form. Blood will be collected by finger prick (in very young children, heel sticks may be substituted for finger pricks) for thick smear, collection of plasma for PK studies, and filter paper samples. If a pregnant woman or parent/guardian of a child reports a fever in the last 24 hours or the patient has a documented temperature $\geq 38.0^{\circ}\text{C}$ tympanic, the patient's thick blood smear will be read immediately and if positive the patient will be diagnosed and treated for malaria (see section 6.2). Phlebotomy for routine laboratory tests (CBC and ALT) to monitor for potential adverse events from study medications and for immunology studies will be performed every 8 weeks in pregnant women and every 16 weeks in children. Screening for non-malaria parasitic infections will be performed once in pregnant women after the 1st trimester at the time routine mebendazole is administered and in children at 1 year of age.

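### Section 6.1 rules out a thick smear at unscheduled clinic visits without fever and makes no exception for Appendix F severe or danger signs: a narrow patient-safety gap

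*Protocol*

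**What the plan says.** Protocol section 6.1 sets the testing rule for every study-clinic visit. A participant with a tympanic temperature of at least 38.0°C, or with fever reported in the past 24 hours, has a thick smear. For everyone else: "If the patient is afebrile and does not report a recent fever, a thick blood smear will not be obtained". One exception follows, the routine schedule of section 6.5. The same section tells parents to "bring their child to the study clinic for all medical care" and to avoid outside medications.

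Section 6.3 repeats the fever condition: "During follow-up for non-malarial illnesses, blood smears will be done at the discretion of the study physician if the subjects are febrile" or report fever in the past 24 hours. The schema also starts from fever: "Patients presenting with a new episode of fever will undergo standard evaluation for the diagnosis of malaria".

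Section 6.2 lists fever as a criterion for uncomplicated malaria only. Complicated malaria needs evidence of severe malaria plus parasitemia, or, as its second criterion, "Danger signs present in children (Appendix F) and parasitemia". Neither list in Appendix F contains fever. On treatment, 6.2 says: "Patients with complicated malaria will be prescribed quinine or artesunate according to national malaria treatment guidelines".

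**The concern.** The protocol describes a serious form of malaria without requiring fever, then withholds the confirming test when fever is absent. A child brought in between routine visits with convulsions, lethargy or vomiting of everything, with no fever measured or reported, meets the clinical half of the complicated-malaria definition. The parasitemia half cannot be established at that visit if 6.1 is followed.

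Two things are at stake. The first is clinical: the drugs prescribed for complicated malaria could be delayed in a parasitemic child. The second is ascertainment: complicated malaria is a secondary outcome for hypothesis 2 (section 8.2.2, Table 8) and for hypotheses 3A and 3B (section 8.3.2), and an episode that is never tested is not counted. The primary outcome for these hypotheses counts all treatments for malaria (8.2.1, 8.3.1), so such an episode would be lost there too.

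**Working it through.** The point is textual; no sample-size, power or error-rate figure is involved. The check follows one case through the protocol: a child at an unscheduled daytime visit, temperature below 38.0°C, no fever reported in 24 hours, one Appendix F sign, parasites in the blood.

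1. **Section 6.1.** It covers each clinic visit. The case is neither febrile nor on the routine schedule, so no smear is taken. Severe and danger signs are not mentioned as exceptions.

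2. **Section 6.3.** The child is managed for a non-malarial illness in the clinic or referred to Tororo District Hospital. A discretionary smear during follow-up again requires fever or reported fever. Referral may lead to a smear, but none is required.

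3. **Section 6.4.** This covers after-hours care at the hospital. It does not apply to a daytime clinic visit.

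4. **Section 6.5.** Routine four-weekly visits include a thick smear whatever the temperature, so parasites may be found later. For participants with fever or reported fever, 6.5 says that the "thick blood smear will be read immediately and if positive the patient will be diagnosed and treated for malaria". It states no immediate reading for an afebrile child, even one who shows an Appendix F sign at the routine visit.

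5. **Section 6.14.** Grade 3 or 4 adverse events call for a work-up to exclude other causes. Under Appendix J, coma is grade 4, lethargy that prevents usual activities is grade 3, and a pediatric hemoglobin below 6.5 g/dL is grade 4, which includes the Appendix F threshold of below 5. But a pediatric seizure lasting under 5 minutes with a post-ictal state under 24 hours is grade 1, while fewer than 3 convulsions in 24 hours is an Appendix F danger sign. The work-up therefore does not reach every danger sign. Adverse-event monitoring ends one month after study drugs stop (7.1.2), so it also leaves most of the 24-36 month period of hypothesis 3B uncovered.

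6. **Section 6.2, treatment failure.** Items b, c and d each require fever or reported fever. Item a, complicated malaria 1-14 days after an earlier diagnosis, does not. If the child was diagnosed with malaria within the past 14 days, failure under item a could not be recognised at this visit either.

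No section supplies the missing exception. Steps 2 to 5 give routes by which the child may still be tested, but none is written as an exception to 6.1.

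**Size.** The protocol gives neither the afebrile share of Appendix F presentations nor the share referred to hospital, and no planned rate of complicated malaria. A count of missed episodes cannot be derived.

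**The case against.** The strongest reply is that nothing conflicts. Section 6.2 begins with patients whose malaria is already laboratory-confirmed and then classifies all episodes, so complicated malaria can be read as a severity class for detected episodes, with detection triggered by fever throughout. That reading is tenable, although item a of the treatment-failure list sits less easily with it. A reader might infer a strict contradiction between 6.1 and 6.2; the text does not establish one. The testing gap remains on either reading.

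A reader might also infer that the child is left without care. That is not supported. Section 6.3 provides for standardized algorithms, whose content is not shown, or hospital referral. The study clinic lies within the hospital complex, nothing applies the 6.1 rule to hospital staff, and study personnel visit the hospital daily (6.4). The case needs an unscheduled daytime visit, no fever, an Appendix F sign, parasitemia and no referral, all together. This makes the gap narrow without closing it.

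Finally, the remedy has a statistical risk of its own. Asymptomatic parasitemia is expected here and is itself a secondary outcome (8.2.2). Testing afebrile children with non-specific signs would turn some incidental parasitemia into counted malaria, possibly at different rates by arm if DP frequency changes parasite prevalence. This stands, and the fix must handle it.

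**Conclusion.** The point holds as a low-severity patient-safety correction. Section 6.1, reinforced by 6.3, states a rule which, if followed literally, denies a smear to an afebrile participant with an Appendix F sign at an unscheduled study-clinic visit. It could delay quinine or artesunate and miss a few episodes of complicated malaria.

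The number is unknown and probably small. A reader might infer bias in the comparisons of monthly with q 3 monthly DP, or of the pregnancy regimens in hypothesis 3A. The documents do not support that: the rule is identical in all blinded arms, and no effect on any comparison, power figure or conclusion is shown.

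The verdict assumes that clinic staff follow 6.1 as written and that the unseen algorithms in 6.3 do not already require a smear for these signs. If they do, the amendment only brings 6.1 into line with practice.

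**What to change.** Add to section 6.1, and mirror in 6.3 and 6.5: any participant with an Appendix F severe criterion, or any child with an Appendix F danger sign, has a thick smear taken and read immediately regardless of fever, and is managed under 6.2 if it is positive. Leave the definition of complicated malaria unchanged.

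Record for each such episode whether fever was measured or reported. Report a sensitivity analysis restricted to febrile episodes for both malaria incidence and complicated malaria, so that any arm-dependent counting of incidental parasitemia can be seen.

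The cost is one sentence in three places, a few extra finger-prick or heel-stick smears using the existing test, one case-record field and one additional analysis for each of the two outcomes. The price in interpretation is that some children with non-specific signs and incidental parasites will be treated and counted as having malaria; the febrile-only analysis shows how much that matters.

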6.2. Diagnosis and Management of Malaria

Patients found to have malaria based on laboratory confirmation will have a second finger prick for a thin smear (to determine parasite species), hemoglobin measurement using a portable spectrophotometer (HemoCue), and collection of plasma for future PK studies. All episodes of malaria will be classified as uncomplicated or complicated based on the following criteria:

Uncomplicated malaria (all of the following)

- 1) Fever ($\geq 38.0^{\circ}\text{C}$ tympanic) or history of fever in the previous 24 hours
- 2) Positive thick blood smear
- 3) Absence of complicated malaria

Complicated malaria (any of the following)

- 1) Evidence of severe malaria (Appendix F) and parasitemia
- 2) Danger signs present in children (Appendix F) and parasitemia

Episodes of malaria will also be classified into the following categories according to the timing of previous malaria episodes for treatment purposes:

1. New episodes of malaria will be defined as any first episode or any episode occurring > 14 days after the diagnosis of a previous episode
2. Treatment failures will be defined as any of the following:
 - a. Complicated malaria occurring 1-14 days after the diagnosis of a previous episode
 - b. Fever ($\geq 38.0^{\circ}\text{C}$ tympanic) or history of fever in the previous 24 hours with a parasite density \geq the parasite density of an episode of malaria diagnosed 2 days prior

- c. Fever ($\geq 38.0^{\circ}\text{C}$ tympanic) or history of fever in the previous 24 hours with a parasite density $\geq 25\%$ of the parasite density of an episode of malaria diagnosed 3 days prior
- d. Fever ($\geq 38.0^{\circ}\text{C}$ tympanic) or history of fever in the previous 24 hours with a positive thick blood smear of any parasite density occurring 4-14 days after the diagnosis of a previous episode

All patients diagnosed with new episodes of uncomplicated malaria will be prescribed AL, the recommended first-line treatment in Uganda for children and pregnant women in their 2nd or 3rd trimester. Patients with complicated malaria will be prescribed quinine or artesunate according to national malaria treatment guidelines. Children who are less than 4 months of age or weigh $<5\text{kg}$, will be treated with quinine for uncomplicated malaria in accordance with the Uganda Ministry of Health Guidelines. Patients with treatment failure within 14 days following treatment with AL will be prescribed quinine according to national malaria treatment guidelines. Patients with treatment failure within 14 days following treatment with quinine or artesunate will be treated with quinine plus clindamycin or artesunate.

